7.1.1.4 Medical History

A medical history will be obtained by the investigator or qualified designee. Medical history will include all active conditions, and any condition diagnosed within the prior 10 years that are considered to be clinically significant by the investigator. Details regarding the disease for which the subject has enrolled in this trial will be recorded separately and not listed as medical history.

Prior acute and/or chronic Graft versus Host Disease, maximum grade, and dates will be collected.

7.1.1.5 Prior and Concomitant Medications Review

7.1.1.5.1 Prior Medications

The investigator or qualified designee will review prior medication use and record prior medication taken by the subject within 28 days before starting the trial. Treatment for the disease for which the subject has enrolled in the trial will be recorded separately and not listed as a prior medication.

7.1.1.5.2 Concomitant Medications

The investigator or qualified designee will record medication, if any, taken by the subject during the trial through the Safety Follow-up visit.

Record all medications taken for SAEs and ECIs as defined in Section 7.2.

7.1.1.5.3 Prior Cancer Treatment Details

The investigator or qualified designee will review all prior cancer treatments including but not limited to systemic treatments, prior transplantation, radiation, and surgeries and record in the trial database.

7.1.1.5.4 Subsequent Antineoplastic Therapy

The investigator or qualified designee will review all new antineoplastic therapy initiated after the last dose of trial treatment.

Collect transplant parameters after trial treatment to include the conditioning regimen, date, and type of transplant.

If a subject initiates a new antineoplastic therapy within 30 days after the last dose of trial treatment, the 30-day Safety Follow-up visit must occur before the first dose of the new therapy. Once new antineoplastic therapy has been initiated, the subject will move into survival follow-up.

7.1.1.6 Assignment of Screening Number

All consented subjects will be given a unique screening number that will be used to identify the subject for all procedures that occur prior to randomization or treatment allocation. Each subject will be assigned only one screening number. Screening numbers must not be re-used for different subjects.

Any subject who is screened multiple times will retain the original screening number assigned at the initial screening visit.

Specific details on the screening visit requirements (screening/rescreening) are provided in Section 7.1.5.

7.1.1.7 Assignment of Treatment/Randomization Number

All eligible subjects will be allocated, by non-random assignment, and will receive a treatment/randomization number. The treatment/randomization number identifies the subject for all procedures occurring after treatment allocation/randomization. The assigned screening number will become the subjects' treatment/randomization number. Once a treatment/randomization number is assigned to a subject, it can never be re-assigned to another subject.

A single subject cannot be assigned more than 1 treatment/randomization number.

7.1.1.8 Trial Compliance

Interruptions from the protocol specified treatment plan for ≥ 3 weeks require consultation between the investigator and the Sponsor and written documentation of the collaborative decision on subject management.

Administration of dinaciclib and pembrolizumab will be done by the investigator and/or trial staff. The total volume of pembrolizumab infused will be compared to the total volume prepared to determine compliance with each dose administered.

The instructions for preparing and administering dinaciclib and pembrolizumab will be provided in the Pharmacy Manuals.

7.1.2 Clinical Procedures/Assessments

7.1.2.1 Oncologic Disease Details

The investigator or qualified designee will obtain prior and current details regarding oncologic disease status.

DLBCL subtypes, including germinal center B-cell–like (GCB), activated B-cell–like (ABC), and unclassified (not fitting the criteria for either ABC or GCB DLBCL subtypes), are requested. Other known pathology and biology parameters, such as T-cell/histiocyte-rich B-cell lymphoma, Epstein-Barr virus positive lymphoma, MYC, B-cell lymphoma 2 (BCL2) gene rearrangement, expression and MYC gene alterations, should be recorded if data are available.

7.1.2.2 Full Physical Exam

The investigator or qualified designee will perform a complete physical exam during the screening period. At this visit, clinically significant abnormal findings should be recorded as medical history. A full physical exam should be performed during screening and repeated as per the frequency defined in the Trial Flow Chart (Section 6.0). After the first dose of trial treatment, new clinically significant abnormal findings should be recorded as AEs.

7.1.2.3 Electrocardiogram

A standard 12-lead electrocardiogram will be performed using local standard procedures at screening. Clinically significant abnormal findings should be recorded as medical history.

7.1.2.4 Vital Signs

The investigator or qualified designee will take vital signs at screening, prior to the administration of each dose of trial treatment and at treatment discontinuation as specified in the Trial Flow Chart (Section 6.0). Vital signs should include temperature, pulse, respiratory rate, weight and blood pressure. Height will be measured at screening only.

7.1.2.5 Eastern Cooperative Oncology Group Performance Status

The investigator or qualified designee will assess ECOG status (Section 12.4) at screening, on Day 1 of Q3W cycle and discontinuation of trial treatment as specified in the Trial Flow Chart (Section 6.0).

7.1.2.6 Adverse Event Monitoring

The investigator or qualified designee will assess each subject to evaluate for potential new or worsening AEs as specified in the Trial Flow Chart and more frequently if clinically indicated. AEs will be graded and recorded throughout the trial and during the follow-up period according to National Cancer Institute’s CTCAE Version 4.0 (Section 12.11). Toxicities will be characterized in terms regarding seriousness, causality, toxicity grading, and action taken with regard to trial treatment.

Refer to Section 7.2 for detailed information regarding the assessment and recording of AEs.

7.1.2.7 Criteria for Assessment of Disease

Antitumor activity of dinaciclib and pembrolizumab will be evaluated locally using the following criteria:

- CLL: iwCLL guidelines [1]
- MM: International uniform response criteria for multiple myeloma [2]
- DLBCL: Revised Response Criteria for Malignant Lymphoma [3]

7.1.2.7.1 Disease Assessment During Trial

Disease assessments should be performed locally per the frequency defined in the Trial Flow Chart (Section 6.0). There is a \pm 7-day window for assessments performed after Day 1.

Disease assessments or scans should not be delayed for delays in cycle starts.

Images and/or laboratory assessments may be requested by the Sponsor for independent review.

7.1.2.7.2 Disease Assessment of Immunotherapeutic Agents

Immunotherapeutic agents such as pembrolizumab may produce antitumor effects by potentiating endogenous cancer-specific immune responses, which may be functionally anergic. The response patterns seen with such an approach may extend beyond the typical time course of responses seen with cytotoxic agents, and can manifest a clinical response after an initial increase in tumor burden or even the appearance of new lesions. Standard response assessment criteria may not provide a complete response assessment of immunotherapeutic agents such as pembrolizumab. Therefore, in the setting where a subject's assessment shows PD, trial drug may be continued at the discretion of the investigator until the next disease response assessment provided that the subject's clinical condition is stable. However, imaging should occur at any time when there is clinical suspicion of progression.

Refer to Section 7.1.2.7.3 for confirmation assessment requirements when a subject's disease response assessment shows PD.

7.1.2.7.3 Disease Progression Assessments

A subject with progression of disease documented at a disease response assessment may continue trial treatment until the next response assessment, provided the subject's clinical condition is stable. However, a response assessment should occur at any time where there is clinical suspicion of progression.

Subjects may only receive treatment while waiting for confirmation of PD if the following criteria are met:

- Absence of signs and symptoms (including worsening of laboratory values) indicating disease progression
- No decline in ECOG performance status

- Absence of rapid progression of disease
- Absence of progressive tumor at critical anatomical sites

After the first disease response assessment, it is at the discretion of the investigator to keep a clinically stable subject on trial treatment or to stop trial treatment until a repeat assessment is performed. Subjects who are deemed clinically unstable after first disease response assessment should not continue trial treatment and must be discontinued from the trial. Subjects who are deemed clinically unstable are not required to have repeat imaging for confirmation.

For subjects noted to have progression of disease at a time point beyond the disease response assessment, the investigator, upon consultation with the Sponsor, may keep a clinically stable subject on trial treatment as long as the subject is deriving clinical benefit.

Sponsor recommendation is that the subject should be on trial treatment for at least 8 weeks in order to confirm disease progression and at least 2 consecutive assessments with minimum of 2 weeks of time between assessments are required unless there is a clinical compromise in which case the subject may be discontinued after consultation with the Sponsor.

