1.0 TRIAL SUMMARY

Abbreviated Title	Phase Ib trial of pembrolizumab (MK-3475) in combination with dinaciclib (MK-7965) in subjects with hematologic malignancies (KEYNOTE-155)
Trial Phase	Phase Ib
Clinical Indication	
Treatment of subjects with relapsed or refractory chronic lymphocytic leukemia, multiple myeloma (rrMM), or diffuse large B-cell lymphoma (rrDLBCL).
 
Note: The rrMM cohort was closed to enrollment on 07-AUG-2017 due to lack of efficacy, and all subjects with rrMM were discontinued from treatment. Remaining subjects with rrMM are in survival follow-up.
 
Note: The rrCLL cohort was closed to enrollment on 30-APR-2019 due to lack of accrual, and all subjects with rrCLL have discontinued from treatment. Remaining subjects with rrCLL are in survival follow-up.

Trial Type	Interventional
Type of control	No treatment control
Route of administration	Intravenous (IV)
Trial Blinding	Unblinded Open-label
Treatment Groups	Combination of pembrolizumab and dinaciclib
Number of trial subjects	Approximately 102 to a maximum of 138 subjects will be enrolled.
Estimated duration of trial	The sponsor estimates that the trial will require approximately 36 months from the time the first subject signs the informed consent until the last subject's last study-related phone call or visit.
Duration of Participation	Each subject will participate in the trial for up to approximately 26 months. Trial participation is defined as the period from the time the subject signs the Informed Consent Form through the final contact. After a screening phase of 28 days, each subject will receive combination treatment for a maximum of 35 cycles (approximately 2 years) or until documented disease progression by investigator assessment, unacceptable adverse event(s), intercurrent illness that prevents further administration of treatment, subject withdraws consent, pregnancy of the subject, noncompliance with trial treatment or procedure requirements, or administrative reasons. After the end of treatment each subject will be followed for 30 days for a Safety Follow-Up Visit. Subjects who discontinue for reasons other than disease progression will have post-treatment follow-up for disease status until disease progression, initiating a non-trial cancer treatment, withdrawing consent, or becoming lost to follow-up. All subjects will be followed by telephone for overall survival until death, withdrawal of consent, or the end of the trial.

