5.8 Subject Withdrawal/Discontinuation Criteria

5.8.1 Discontinuation of Treatment

Discontinuation of treatment does not represent withdrawal from the trial.

As certain data on clinical events beyond treatment discontinuation are important to the study, they must be collected through the subject's last scheduled follow-up, even if the subject has discontinued treatment. Therefore, all subjects who discontinue trial treatment prior to completion of the treatment period will still continue to participate in the trial as specified in Section 6.0 - Trial Flow Chart and Section 7.1.5.3 – Post Treatment Visits.

Subjects may discontinue treatment at any time for any reason or be dropped from treatment at the discretion of the investigator should any untoward effect occur. In addition, a subject may be discontinued from treatment by the investigator or the Sponsor if treatment is inappropriate, the trial plan is violated, or for administrative and/or other safety reasons. Specific details regarding procedures to be performed at treatment discontinuation are provided in Section 7.1.4 – Other Procedures.

A subject must be discontinued from treatment but continue to be monitored in the trial for any of the following reasons:

- The subject or subject's legally acceptable representative requests to discontinue treatment.
- Confirmed radiographic disease progression outlined in Section 7.1.2.7 (exception if the Sponsor approves treatment continuation).
- Unacceptable AEs as described in Section 7.2.
- Any progression or recurrence of any malignancy, or any occurrence of another malignancy that requires active treatment. Exceptions include basal cell carcinoma of

the skin, squamous cell carcinoma of the skin, or in situ cervical cancer that has undergone potentially curative therapy.

- Intercurrent illness other than another malignancy as noted above that prevents further administration of treatment.
- Recurrent Grade 2 pneumonitis.
- A confirmed positive serum pregnancy test.
- Noncompliance with trial treatment or procedure requirements.
- Investigator's decision to withdraw the subject.

For subjects who are discontinued from treatment but continue to be monitored in the trial, see Section 6.0 – Trial Flow Chart, and Section 7.1.5.3 – Post Treatment Visits for those procedures to be completed at each specified visit.

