5.8.2 Withdrawal from the Trial

A subject must be withdrawn from the trial if the subject or subject's legally acceptable representative withdraws consent from the trial.

If a subject withdraws from the trial, they will no longer receive treatment or be followed at scheduled protocol visits.

Specific details regarding procedures to be performed at the time of withdrawal from the trial including the procedures to be performed should a subject repeatedly fail to return for scheduled visits and/or if the study site is unable to contact the subject, as well as specific details regarding withdrawal from Future Biomedical Research are outlined in Section 7.1.4 – Other Procedures.

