7.1.5.4.2 Survival Follow-up

Once a subject experiences confirmed disease progression or starts a new antineoplastic therapy, the subject moves into the survival follow-up phase and should be contacted by telephone every 12 weeks (\pm 14 days) to assess for survival status until death, withdrawal of consent, or the end of the trial, whichever occurs first. The first survival follow-up assessment should be scheduled as described below:

For participants who discontinue treatment intervention and who will not enter the efficacy follow-up phase, the first survival follow-up assessment will be scheduled 12 weeks after the discontinuation visit and/or safety follow-up visit (whichever is last).

For participants who completed assessments in the efficacy follow-up phase, the first survival follow-up assessment will be scheduled 12 weeks after the last efficacy assessment follow-up visit has been performed.

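### Section 7.1.2.7.3 takes clinically unstable progressors out of the trial, while other sections keep them in survival follow-up; read literally, it would overstate OS

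*Combined protocol and SAP*

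**What the plan says.** Section 7.1.2.7.3 covers subjects with progression at a disease response assessment. For the unstable ones it states: "Subjects who are deemed clinically unstable after first disease response assessment should not continue trial treatment and must be discontinued from the trial". It then waives the confirmatory scan: "Subjects who are deemed clinically unstable are not required to have repeat imaging for confirmation".

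Other sections point the other way:

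- Section 5.8.1: "Discontinuation of treatment does not represent withdrawal from the trial". It introduces its list of mandatory reasons for stopping treatment, which includes progression, with: "A subject must be discontinued from treatment but continue to be monitored in the trial for any of the following reasons".
- Section 5.8.2 gives one mandatory ground for leaving the trial: "A subject must be withdrawn from the trial if the subject or subject's legally acceptable representative withdraws consent from the trial". The consequence is: "If a subject withdraws from the trial, they will no longer receive treatment or be followed at scheduled protocol visits".
- Section 1.0: "All subjects will be followed by telephone for overall survival until death, withdrawal of consent, or the end of the trial".
- Section 7.1.5.4.2: "Once a subject experiences confirmed disease progression or starts a new antineoplastic therapy, the subject moves into the survival follow-up phase". It also schedules a first survival call for participants who stop treatment and do not enter efficacy follow-up.
- Section 7.1.2.8.3 (DLBCL) cites 7.1.2.7.3 as one of the places that define when trial treatment is discontinued. It says nothing there about leaving the trial.

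For the analysis, Section 8.4.1 defines OS from first dose to death from any cause. Table 19 estimates it by Kaplan-Meier in the ASaT population, with censoring at the last assessment. No sensitivity analysis for informative censoring is described.

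**The concern.** The disputed sentence names trial treatment and the trial separately and requires an exit from both. Elsewhere the protocol treats discontinuing from the trial as the end of participation. Section 5.10 lists it beside loss to follow-up among the events that end the trial for the last subject, and Section 7.1.4.1 calls for final-visit activities at that point. A site that used the terms consistently would therefore stop the survival calls.

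The subjects affected have just progressed and are clinically unstable, so their short-term mortality is likely to be the highest in the cohort. Kaplan-Meier assumes that a censored subject has the same future risk as those still followed. Censoring this group at progression breaks that assumption, and the error runs upward.

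A related gap is that Section 7.1.5.4.2 and footnote g of the Trial Flow Chart (Section 6.0) open survival follow-up on confirmed progression or new therapy. Section 7.1.2.7.3 waives confirmation for exactly these subjects, so the entry trigger does not clearly reach them.

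**Working it through.** **Step 1. Where an unstable progressor goes under each section.**

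| Section | Treatment | In the trial? | Survival follow-up? |
|---|---|---|---|
| 7.1.2.7.3, read literally | stops | no | no |
| 5.8.1 | stops | yes, monitored | yes, through scheduled follow-up |
| 5.8.2 | – | leaving is mandatory only on withdrawn consent | – |
| 1.0 | – | yes | yes, to death, withdrawn consent or end of trial |
| 7.1.5.4.2 | stopped | yes | yes; trigger worded as confirmed progression or new therapy |
| 7.1.2.8.3 (DLBCL) | stops, citing 7.1.2.7.3 | not addressed | not addressed |

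The first row cannot hold together with Sections 5.8.1, 1.0 and 7.1.5.4.2.

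**Step 2. Size if the first row were followed.** The plan states no OS rate, no OS-based sizing and no share of unstable subjects, so there is no figure of its own to reproduce.

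From the documents: the first scan falls at about 9 weeks for CLL and DLBCL (Sections 7.1.2.8.1 and 7.1.2.8.3), and there are 30 subjects per cohort (Section 8.8).

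Assumed: 90% alive at week 9; exponential survival afterwards, with median 12 months if stable (range 9 to 18) and 2 months if unstable (range 1 to 3); a share f of those alive at week 9 is unstable and is censored then.

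- Week 9 = 63 / 30.4375 = 2.07 months, leaving 12 − 2.07 = 9.93 months.
- Stable subjects: 2^(−9.93/12) = 0.5635. Unstable subjects: 2^(−9.93/2) = 0.0320.
- True 12-month OS = 0.90 × [(1 − f) × 0.5635 + f × 0.0320].
- Large-sample Kaplan-Meier with the unstable censored = 0.90 × 0.5635 = 50.7%, whatever f is.
- Overstatement = 0.90 × f × (0.5635 − 0.0320) = 0.478 × f.

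| f | True 12-month OS | Kaplan-Meier | Overstatement (before rounding) | True median OS | Kaplan-Meier median |
|---|---|---|---|---|---|
| 10% | 45.9% | 50.7% | 4.8 points | 10.6 months | 12.2 months |
| 20% | 41.1% | 50.7% | 9.6 points | 9.0 months | 12.2 months |
| 30% | 36.4% | 50.7% | 14.4 points | 7.5 months | 12.2 months |

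A simulation of 4,000 cohorts of 30 gave the same 4.8, 9.6 and 14.4 points. Over the assumed ranges, with f from 5% to 40%, the overstatement runs from 1.6 to 24.5 points.

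**Step 3. A second model.** Here unstable subjects are censored at progression whenever it occurs. Median PFS is 3 to 4 months, and median survival after progression is 8 months (stable) or 2 months (unstable), all assumed. The overstatement is about 5, 10 and 15 points at 10%, 20% and 30% unstable; for example, 51% reads as 61% at 20% unstable and a median PFS of 4 months. Median OS is overstated by about 1 to 4 months.

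**Step 4. If Sections 1.0, 5.8.1 and 7.1.5.4.2 are followed.** No unstable subject is censored for this reason, f = 0, and the overstatement is zero.

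**The case against.** A reader might infer that the protocol removes these subjects from survival follow-up and that the trial's OS is therefore biased. The documents do not support that. Sections 1.0, 5.8.1 and 7.1.5.4.2 keep such subjects in, and Section 7.1.2.8.3 reads 7.1.2.7.3 as a rule about treatment. Loose wording is a plausible explanation: Section 7.1.3.2 has subjects with a positive pregnancy test discontinued from the trial, while Sections 5.7.3 and 5.8.1 make the same event a treatment discontinuation with continued monitoring. The no-further-visits consequence in Section 5.8.2 is written for a subject who withdraws, and extending it to an investigator's decision is an inference. Section 7.1.5.4.3 also lets the sponsor request survival status for participants with no scheduled contact. All of this stands, and it makes the bias conditional. It does not remove the contradiction: the sentence is mandatory, Section 5.10 gives its term a terminal meaning, and the 7.1.5.4.3 check is at the sponsor's discretion.

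The sentence is also limited to the first disease response assessment, and the paragraph on later progression does not mention leaving the trial. Read literally, fewer subjects are affected than in Step 3, and f in Step 2 must be taken as the share unstable at the first assessment only. This stands.

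The impact is bounded. OS is a single-arm, descriptive secondary endpoint with no hypothesis test (Section 8.3). With 30 subjects and OS near 50%, the 95% interval is about ±18 points before any censoring (1.96 × √(0.25/30) = 0.179). Table 19 counts missing responses as non-response, so ORR is protected. These facts limit the consequence, but an interval around a biased estimate does not show the bias.

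Finally, the confirmed-progression trigger is not a complete gap. Section 7.1.5.4 sends subjects who stop for a reason other than confirmed progression into efficacy follow-up, and 7.1.5.4.2 provides calls for those who do not enter it. Both routes depend on the subject still being in the trial.

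**Conclusion.** This is an internal contradiction about follow-up that needs correction. It carries a conditional risk to OS, and no loss of OS data is established. If the sentence were applied literally, censoring would be informative and OS would be overstated. The size is illustrative: zero if the other sections govern, and about 5, 10 or 14 to 15 points on 12-month OS if 10%, 20% or 30% of subjects are dropped, with less if only the first assessment counts. Apart from the 9-week scan time and the cohort size, every input to those figures is assumed. The direction of the error needs only that unstable progressors die sooner than the subjects still followed. No view is taken on when treatment should stop.

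**What to change.** 1. In Section 7.1.2.7.3, replace only the closing clause of the sentence, the one on leaving the trial, with a statement that these subjects remain in the trial for survival follow-up under Section 7.1.5.4.2. Leave the treatment-stopping wording as it is. This brings the section into line with Sections 1.0, 5.8.1, 5.8.2 and 7.1.5.4.2.
2. In Section 7.1.5.4.2 and Trial Flow Chart footnote g, extend the confirmed-progression trigger to subjects whose progression was not confirmed because repeat imaging was not required.
3. Before database lock, identify any subject already removed under this sentence and obtain survival status under Section 7.1.5.4.3, where consent allows. Report how many there were.

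The cost is two short wording changes and one status check. Telephone follow-up is already planned for all subjects. The rrMM and rrCLL cohorts have stopped treatment, so the reworded sentence can affect future conduct only in rrDLBCL; the status check applies to all three cohorts.
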